8.6 Treatment of Ipilimumab-Related Isolated Drug Fever

In the event of isolated drug fever, the investigator must use clinical judgment to determine if the fever is related to the ipilimumab or to an infectious etiology. If a patient experiences isolated drug fever, for the next dose, pre-treatment with acetaminophen or non-steroidal anti-inflammatory agent (investigator discretion) should be instituted and a repeated antipyretic dose at 6 and 12 hours after ipilimumab infusion, should be administered. The infusion rate will remain unchanged for future doses. If a patient experiences recurrent isolated drug fever following premedication and post dosing with an appropriate antipyretic, the infusion rate for subsequent dosing should be decreased to 50% of the previous rate. If fever recurs following infusion rate change, the investigator should assess the patient's level of discomfort with the event and use clinical judgment to determine if the patient should receive further ipilimumab.

8.7 Monitoring and Management of Immune-mediated Adverse Reactions

Immune-mediated Enterocolitis

The clinical presentation of GI immune-related AEs included diarrhea, increase in the frequency of bowel movements, abdominal pain, or hematochezia, with or without fever. However, inflammation may occur in any part of the GI tract including esophagitis and gastritis. Fatalities due to GI perforation have been reported in clinical trials of ipilimumab.

Patients should be carefully monitored for GI symptoms that may be indicative of immune-related colitis, diarrhea, or GI perforation. Diarrhea or colitis occurring after initiation of ipilimumab therapy should be evaluated to exclude infectious or alternate etiologies. In clinical trials, immune-related colitis was associated with evidence of mucosal inflammation, with or without ulcerations, and lymphocytic infiltration.

Monitor patients for signs and symptoms of enterocolitis (such as diarrhea, abdominal pain, mucus or blood in stool, with or without fever) and bowel perforation (such as peritoneal signs and ileus). In symptomatic patients, rule out infectious etiologies and consider endoscopic evaluation to establish etiology and for persistent or severe symptoms. C.difficile toxin has been detected in several patients with colitis and may be an independent entity or may co-exist with ipilimumab induced inflammatory colitis.

Withhold ipilimumab and/or nivolumab dosing for any patients with enterocolitis pending evaluation; administer anti-diarrheal treatment and, if persistent evaluate with colonoscopy and initiate systemic corticosteroids at a dose of 0.5 mg/kg/day prednisone or equivalent.

Permanently discontinue ipilimumab and nivolumab in patients with severe enterocolitis and initiate systemic corticosteroids at a dose of 1 to 2 mg/kg/day of prednisone or equivalent. Upon improvement to Grade 1 or less, initiate corticosteroid taper and continue to taper over at least one month. In clinical trials, rapid corticosteroid tapering has resulted in recurrence or worsening symptoms of enterocolitis in some patients.

Patients have been treated with anti-TNF agents for persistent colitis not responding to steroids.

Please note autoimmune pancreatitis may cause abdominal pain and should be included in all evaluations. Enteritis may occur occasionally with other autoimmune events including hepatitis, pancreatitis, and endocrine insufficiency, which should be evaluated as clinically indicated.

Immune-mediated Hepatitis and Pancreatitis

Hepatic immune-related AEs were mostly clinically silent and manifested as transaminase or bilirubin laboratory abnormalities. Fatal hepatic failure has been reported in clinical trials of ipilimumab. Serum transaminase and bilirubin must be evaluated before each dose of ipilimumab and nivolumab as early laboratory changes may be indicative of emerging immune-related hepatitis/ pancreatitis and elevations in liver function tests (LFTs) **may develop in the absence of clinical symptoms**. Increase in LFT or total bilirubin should be evaluated to exclude other causes of hepatic injury, including infections, disease progression, or other medications, and monitored until resolution. Liver biopsies from patients who had immune-related hepatotoxicity showed evidence of acute inflammation (neutrophils, lymphocytes, and macrophages).

Monitor liver function tests (hepatic transaminase and bilirubin levels) and assess patients for signs and symptoms of hepatotoxicity/ pancreatitis before each dose of ipilimumab and nivolumab. In patients with hepatotoxicity, rule out infectious or malignant causes and increase frequency of liver function test monitoring until resolution. Withhold ipilimumab and nivolumab in patients with Grade 2 hepatotoxicity.

Permanently discontinue ipilimumab and nivolumab in patients with Grade 3–5 hepatotoxicity/pancreatitis and administer systemic corticosteroids at a dose of 1 to 2 mg/kg/day of prednisone or equivalent. When liver function tests show sustained improvement or return to baseline, initiate corticosteroid tapering and continue to taper over 1 month. Across the clinical development program for ipilimumab, mycophenolate

treatment has been administered in patients who have persistent severe hepatitis despite high-dose corticosteroids.

Immune-mediated Dermatitis

Skin immune-related AEs presented mostly frequently as a rash and/or pruritus. Some patients reported vitiligo associated with ipilimumab administration. Fatal toxic epidermal necrolysis has been reported in clinical trials of ipilimumab.

Monitor patients for signs and symptoms of dermatitis such as rash and pruritus. Unless an alternate etiology has been identified, signs or symptoms of dermatitis should be considered immune-mediated.

Permanently discontinue ipilimumab and nivolumab in patients with Stevens-Johnson syndrome, toxic epidermal necrolysis, or rash complicated by full thickness dermal ulceration, or necrotic, bullous, or hemorrhagic manifestations. Administer systemic corticosteroids at a dose of 1 to 2 mg/kg/day of prednisone or equivalent. When dermatitis is controlled, corticosteroid tapering should occur over a period of at least 1 month. Withhold ipilimumab and nivolumab dosing in patients with moderate to severe signs and symptoms.

For mild to moderate dermatitis, such as Grade 2 localized rash and pruritus, treat symptomatically. For persistent Grade 2, Grade 3, or greater, topical steroids may be administered. Administer topical or systemic corticosteroids as indicated if there is no improvement of symptoms within 1 week.

Immune-related Neurological Events

Fatal Guillain-Barré syndrome has been reported in clinical trials of ipilimumab. Patients may present with muscle weakness and myasthenia gravis, cranial nerve palsy (n VII Bell's palsy), and aseptic meningitis, encephalopathy. Unexplained motor neuropathy, muscle weakness, or sensory neuropathy lasting more than 4 calendar days should be evaluated and non-inflammatory causes such as disease progression, infections, metabolic syndromes, nerve entrapment, and medications should be excluded as causes.

Withhold ipilimumab and nivolumab dosing in patients with any evidence of neuropathy pending evaluation.

Monitor for symptoms of motor or sensory neuropathy such as unilateral or bilateral weakness, sensory alterations, or paresthesia. Permanently discontinue ipilimumab and nivolumab in patients with severe neuropathy (interfering with daily activities) such as Guillain-Barré-like syndromes. Institute medical intervention as appropriate for management of neuropathy and other neurologic events. Consider initiation of systemic corticosteroids at a dose of 1 to 2 mg/kg/day prednisone or equivalent for severe neuropathies.

Immune-mediated Endocrinopathies

Ipilimumab and/or nivolumab can cause inflammation of endocrine organs including thyroid (Hashimoto's thyroiditis with positive antibodies) and adrenal glands, hypophysitis, hypopituitarism, and resulting thyroid and adrenal insufficiency, low ADH, prolactin, FSH, LH. Hyperthyroid with Graves' disease and positive antibody has been reported. Patients may present with subtle and nonspecific symptoms. The most common clinical presentation includes headache and fatigue. Symptoms may also include visual field defects, behavioral changes, and electrolyte disturbances including hyponatremia and hypotension. Adrenal crisis as a cause of the patient's symptoms should be excluded. Based on the available data with known outcome, most of the patients symptomatically

improved with hormone replacement therapy. Long-term hormone replacement therapy with HC and Synthroid will typically be required for patients developing hypophysitis/hypopituitarism after treatment with ipilimumab alone or with nivolumab. Some patients have regained partial function following steroid treatment.

Monitor patients for clinical signs and symptoms of hypophysitis, adrenal insufficiency (including adrenal crisis), and hyper- or hypothyroidism. Headache is often the first symptoms of hypophysitis. Patients may present with fatigue, headache, mental status changes, loss of libido, abdominal pain, unusual bowel habits, and hypotension, or nonspecific symptoms which may resemble other causes such as brain metastasis or underlying disease. Unless an alternate etiology has been identified, signs or symptoms of endocrinopathies should be considered immune-mediated and drugs withheld pending evaluation. Patients may demonstrate both central (hypophysitis) and peripheral adrenal and thyroid insufficiency. Evaluation of hypophysitis should include pituitary MRI.

Endocrine evaluation, including TSH, should be performed at baseline prior to initial treatment. Monitor thyroid function tests and clinical chemistries at the start of treatment and hold blood for possible evaluation should clinical events require determining baseline function and anti-thyroid antibodies. In a limited number of patients, hypophysitis was diagnosed by imaging studies through enlargement of the pituitary gland.

Withhold ipilimumab and nivolumab dosing in patients symptomatic for hypophysitis. Initiate systemic corticosteroids at a dose of 1 to 2 mg/kg/day of prednisone or equivalent, and initiate appropriate hormone replacement therapy.

Other Immune-mediated Adverse Reactions, Including Ocular Manifestations

Ocular inflammation, manifested as Grade 2 or Grade 3 episcleritis or uveitis, was associated with concomitant diarrhea in a few patients (< 1%) and occasionally occurred in the absence of clinically apparent GI symptoms. Other presumed immune-related AEs reported include, but were not limited to, arthritis/arthralgias, pneumonitis, pancreatitis, autoimmune (aseptic) meningitis, autoimmune nephritis, pure red cell aplasia, noninfective myocarditis, polymyositis, and myasthenia gravis, of which were individually reported for < 1% of patients.

The following clinically significant immune-mediated adverse reactions were seen in less than 1% of ipilimumab-treated patients in Study 1: nephritis, pneumonitis, pulmonary granuloma resembling sarcoidosis, meningitis, pericarditis, uveitis, iritis, ITP, neutropenia and hemolytic anemia.

Across the clinical development program for ipilimumab, the following likely immune-mediated adverse reactions were also reported with less than 1% incidence: myocarditis, angiopathy, temporal arteritis, vasculitis, polymyalgia rheumatica, conjunctivitis, blepharitis, episcleritis, scleritis, leukocytoclastic vasculitis, erythema multiforme, psoriasis, pancreatitis, arthritis, and autoimmune thyroiditis.

Permanently discontinue ipilimumab and nivolumab for clinically significant or severe immune-mediated adverse reactions. Initiate systemic corticosteroids at a dose of 1 to 2 mg/kg/day prednisone or equivalent for severe immune-mediated adverse reactions.

Administer corticosteroid eye drops to patients who develop uveitis, iritis, or episcleritis. Permanently discontinue ipilimumab for immune-mediated ocular disease that is unresponsive to local immunosuppressive therapy.

- a. Overall, immune-related AEs commonly started within 3 to 10 weeks from first dose, were successfully managed in most instances by omitting doses, discontinuing dosing, and/or through administering symptomatic or immunosuppressive therapy, including corticosteroids, as mentioned above and detailed in [Section 7.0](#). Immune-related AEs generally resolved within days to weeks in the majority of patients

8.8 White Blood Cell Growth Factors

If used, white blood cell growth factors, including biosimilars, must be used per ASCO guidelines (<http://jco.ascopubs.org/content/24/19/3187.full>) and NCCN Guidelines® Myeloid Growth Factors (http://www.nccn.org/professionals/physician_gls/pdf/myeloid_growth.pdf).

8.10 Adverse Event Reporting

Toxicities (including suspected reactions) that meet the expedited reporting criteria as outlined in [Section 16.1](#) of the protocol must be reported to the Operations Office, Study Chair and NCI via CTEP-AERS, and to the IRB per local IRB requirements.

CLOSED EFFECTIVE 7/15/2020

9.0 STUDY CALENDAR

9.1 Arm 1

	Pre-registration ^G	Cycle (1 cycle = 21 days)												Follow-up prior to progression	Follow-up after progression
		1			2			3			4				
		Week ^K													
		1	2	3	4	5	6	7	8	9	10	11	12		
PHYSICAL															
History and physical exam	X	X _L		X			X			X				X ^N	X ^Q
Weight and performance status ^R	X	X _L		X			X			X				X ^N	X ^Q
Toxicity notation		X		X			X			X				X ^P	X ^P
Baseline abnormalities		X													
Disease assessments	X												X ^M	X ^N	
Biopsy ^A		X				X									
LABORATORY															
ANC, platelets, and hemoglobin	X	X _L		X			X			X				X ^P	X ^P
AST, ALT, and total bilirubin	X	X _L		X			X			X				X ^P	X ^P
Serum creatinine	X	X _L		X			X			X				X ^P	X ^P
Pregnancy test	X ^H														
Creatinine phosphokinase (CPK), Troponin, and Cardiology consultation ^B	X														
CD4	X ^J														
TSH, Free T4, Free T3 ^C		X		X			X			X					

Calendar continued on next page. Click here for [Footnotes](#)

	Pre-registration ^G	Cycle (1 cycle = 21 days)												Follow-up prior to progression	Follow-up after progression	
		1			2			3			4					
		Week ^K														
		1	2	3	4	5	6	7	8	9	10	11	12			
X-RAYS AND SCANS																
MRI or CT for disease assessment ^S	X													X ^M	X ^N	
Electrocardiogram (ECG) and Echocardiogram (Echo) ^D	X															
SPECIMEN SUBMISSION																
Archival tissue ^E		X														
Tissue block or slides from biopsy		X				X										
Blood ^F		X				X										
Fresh Frozen Tissue from biopsy ^T		X				X										
TREATMENT																
Ipilimumab		X			X			X				X				

Calendar continued on next page. Click here for [Footnotes](#)

Note: Forms are found on the protocol abstract page of the SWOG website (www.swog.org). The schedule for submission of these forms is listed in [Section 14.0](#).

Note: Unless indicated otherwise in the protocol, scheduled procedures and assessments (treatment administration, toxicity assessment for continuous treatment, disease assessment, specimen collection and follow-up activities) must follow the established SWOG guidelines as outlined in <https://swog.org/Visitors/Download/QA/Best%20Practices%20update.pdf>.

Footnotes

- A To be performed on or prior to Day 1 and on Day 21-35 (Day 28 +/- 7 days). The first biopsy should be performed within 28 days prior to Day 1. If it is not feasible to obtain this biopsy, tissue that was collected at any time since demonstrated progression on PD-1 or PD-L1 therapy may be substituted provided that 30 unstained slides are available.
- B Only for patients with symptoms of congestive heart failure (CHF), cardiomyopathy, myocarditis, myocardial infarction, or exposure to cardiotoxic medications. Required pre-registration (see [Section 5.3n](#)). After that, perform as clinically indicated.
- C Free T3 and Free T4 are only required if TSH results are abnormal.
- D Only for patients with a known history of congestive heart failure (CHF), cardiomyopathy, myocarditis, myocardial infarction, exposure to cardiotoxic medications, or with a clinical history suggestive of any of these conditions. Required pre-registration (see [Section 5.3m](#)). After that, perform as clinically indicated.
- E Collected prior to previous anti-PD-1 or anti-PD-L1 treatment
- F To be drawn on or prior to Day 1 (after registration and within 28 days) and on Day 21-35 (Day 28 +/- 7 days). If feasible, Day 1 blood should be drawn on the same day as the baseline tissue biopsy. Day 28 Blood must be drawn on same day as the Day 28 tissue biopsy.
- G Required time frame is detailed in [Section 5.0](#).
- H Only for females of reproductive potential (see [Section 5.3p](#))
- J Only required for patients with a known history of HIV (see [Section 5.3g](#))
- K Weeks measured from start of treatment, provided that the patient does not have any treatment delays
- L If pre-registration exam/lab was performed within 14 days prior to Cycle 1 Day 1, this exam/lab does not need to be repeated on Cycle 1 Day 1.
- M Performed at completion of Week 12
- N Every 12 weeks until progression
- P Every 3 weeks until resolution of adverse events
- Q At least every 6 months (+/- 2 weeks) until 2 years after registration, then annually (+/- 4 weeks) until 3 years after registration.
- R Though weight should be checked at each visit, weight-based dosing should be calculated using baseline weight unless weight has changed from last dose by more than 10%.
- S CT or MRI of the chest, abdomen, and pelvis should be performed at baseline and all subsequent assessments. Additionally, for patients with known assessable scalp or neck disease, a CT or of the head/face/neck should be performed at baseline and all subsequent assessments. Patients with known assessable extremity disease should have the affected extremity also measured by CT or MRI at baseline and all subsequent visits. Patients with a history of central nervous system metastases must have MRI of the brain at baseline and at all subsequent assessments.
- T Select sites will, at each prospective biopsy timepoint, obtain additional cores. See [Section 15.1c.4](#) for details.

9.2 Arm 2: Cycles 1 through 4 (see [Section 9.3](#) for Arm 1 Cycles 5+)

	Pre-registration G	Cycle (1 cycle = 21 days)											
		1			2			3			4		
		Week ^K											
		1	2	3	4	5	6	7	8	9	10	11	12
PHYSICAL													
History and physical exam	X	X ^L		X			X			X			
Weight and performance status ^N	X	X ^L		X			X			X			
Toxicity notation		X		X			X			X			
Baseline abnormalities		X											
Disease assessments	X												X ^M
Biopsy ^A		X				X							
LABORATORY													
ANC, platelets, and hemoglobin	X	X ^L		X			X			X			
AST, ALT, and total bilirubin	X	X ^L		X			X			X			
Serum creatinine	X	X ^L		X			X			X			
Pregnancy test	X ^H												
Creatinine phosphokinase (CPK), Troponin, and Cardiology consultation ^B	X												
CD4	X ^J												
TSH, Free T4, Free T3 ^C		X		X			X			X			

Calendar continued on next page. Click here for [footnotes](#).

	Pre-registration ^G	Cycle (1 cycle = 21 days)											
		1			2			3			4		
		Week ^K											
		1	2	3	4	5	6	7	8	9	10	11	12
X-RAYS AND SCANS													
MRI or CT for disease assessment ^O	X												X ^M
Electrocardiogram (ECG) and Echocardiogram (Echo) ^D	X												
SPECIMEN SUBMISSION													
Archival tissue ^E		X											
Tissue block or slides from biopsy		X				X							
Blood ^F		X				X							
Fresh Frozen Tissue from biopsy ^P						X							
TREATMENT													
Nivolumab 1 mg/kg		X			X			X			X		
Ipilimumab		X			X			X			X		

Click here for [footnotes](#).

Note: Forms are found on the protocol abstract page of the SWOG website (www.swog.org). The schedule for submission of these forms is listed in [Section 14.0](#)

Note: Unless indicated otherwise in the protocol, scheduled procedures and assessments (treatment administration, toxicity assessment for continuous treatment, disease assessment, specimen collection and follow-up activities) must follow the established SWOG guidelines as outlined in <https://swog.org/Visitors/Download/QA/Best%20Practices%20update.pdf>.

Footnotes

- A To be performed on or prior to Day 1 and on Day 21-35 (Day 28 +/- 7 days). The first biopsy should be performed within 28 days prior To Day 1. If it is not feasible to obtain this biopsy, tissue that was collected at any time since demonstrated progression on PD-1 or PD-L1 therapy may be substituted provided that 30 unstained slides are available.
- B Only for patients with symptoms of congestive heart failure (CHF), cardiomyopathy, myocarditis, myocardial infarction, or exposure to cardiotoxic medications. Required pre-registration (see [Section 5.3n](#)). After that, perform as clinically indicated.
- C Free T3 and Free T4 are only required if TSH results are abnormal.
- D Only for patients with a known history of congestive heart failure (CHF), cardiomyopathy, myocarditis, myocardial infarction, exposure to cardiotoxic medications, or with a clinical history suggestive of any of these conditions. Required pre-registration (see [Section 5.3m](#)). After that, perform as clinically indicated.
- E Collected prior to previous anti-PD-1 or anti-PD-L1 treatment. See [Section 15.1](#).
- F To be drawn on or prior to Day 1 (after registration and within 28 days prior) and on Day 21-35 (Day 28 +/- 7 days). If feasible, Day 1 blood should be drawn on the same day as the baseline tissue biopsy. Day 28 blood must be drawn on same day as the Day 28 tissue biopsy.
- G Required time frame is detailed in [Section 5.0](#).
- H Only for females of reproductive potential (see [Section 5.3p](#))
- J Only required for patients with a known history of HIV (see [Section 5.3g](#))
- K Weeks measured from start of treatment, provided that the patient does not have any treatment delays
- L If pre-registration exam/lab was performed within 14 days prior to Cycle 1 Day 1, this exam/lab does not need to be repeated on Cycle 1 Day 1.
- M Performed at completion of Week 12
- N Though weight should be checked at each visit, weight-based dosing should be calculated using baseline weight unless weight has changed from baseline by more than 10%.
- O CT or MRI of the chest, abdomen, and pelvis should be performed at baseline and all subsequent assessments. Additionally, for patients with known assessable scalp or neck disease, a CT or of the head/face/neck should be performed at baseline and all subsequent assessments. Patients with known assessable extremity disease should have the affected extremity also measured by CT or MRI at baseline and all subsequent visits. Patients with a history of central nervous system metastases must have MRI of the brain at baseline and at all subsequent assessments.
- O CT or MRI of the chest, abdomen, and pelvis should be performed at baseline and all subsequent assessments. Additionally, for patients with known assessable scalp or neck disease, a CT or of the head/face/neck should be performed at baseline and all subsequent assessments. Patients with known assessable extremity disease should have the affected extremity also measured by CT or MRI at baseline and all subsequent visits. Patients with a history of central nervous system metastases must have MRI of the brain at baseline and at all subsequent assessments.
- P Select sites will, at each prospective biopsy timepoint, obtain additional core. See [Section 15.1c.4](#) for details.

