		Stevens-Johnson syndrome	
		Toxic epidermal necrolysis	
	Urticaria		
VASCULAR DISORDERS			
	Hypotension		

¹ This table will be updated as the toxicity profile of the agent is revised. Updates will be distributed to all Principal Investigators at the time of revision. The current version can be obtained by contacting [contact]. Your name, the name of the investigator, the protocol and the agent should be included in the e-mail.

² Ipilimumab can result in severe and fatal immune-mediated adverse events probably due to T-cell activation and proliferation. These can include (but are not limited to) autoimmune hemolytic anemia, acquired anti-factor VIII immune response, autoimmune aseptic meningitis, autoimmune hepatitis, autoimmune thyroiditis, hepatic failure, pure red cell aplasia, pancreatitis, ulcerative and hemorrhagic colitis, endocrine disorders (e.g., autoimmune thyroiditis, hyperthyroidism, hypothyroidism, autoimmune hypophysitis/hypopituitarism, and adrenal insufficiency), ocular manifestations (e.g., uveitis, iritis, conjunctivitis, blepharitis, and episcleritis), sarcoid granuloma, myasthenia gravis, polymyositis, and Guillain-Barre syndrome. The majority of these reactions manifested early during treatment; however, a minority occurred weeks to months after discontinuation of ipilimumab especially with the initiation of additional treatments.

³ Late bowel perforations have been noted in patients receiving MDX-010 (ipilimumab) in association with subsequent IL-2 therapy.

⁴ Complications including hyperacute graft-versus-host disease (GVHD), may occur in patients receiving allo stem cell transplant (SCT) after

CLOSED FILE

receiving Ipilimumab (MDX-010). These complications may occur despite intervening therapy between receiving Ipilimumab (MDX-010) and allo-SCT.

- ⁵ In rare cases diplopia (double vision) has occurred as a result of muscle weakness (Myasthenia gravis).
- ⁶ Gastrointestinal hemorrhage includes Anal hemorrhage, Cecal hemorrhage, Colonic hemorrhage, Duodenal hemorrhage, Esophageal hemorrhage, Esophageal varices hemorrhage, Gastric hemorrhage, Hemorrhoidal hemorrhage, Ileal hemorrhage, Intra-abdominal hemorrhage, Jejunal hemorrhage, Lower gastrointestinal hemorrhage, Oral hemorrhage, Pancreatic hemorrhage, Rectal hemorrhage, Retroperitoneal hemorrhage, and Upper gastrointestinal hemorrhage under the GASTROINTESTINAL DISORDERS SOC.
- ⁷ Infection includes all 75 sites of infection under the INFECTIONS AND INFESTATIONS SOC.

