7.2 Treatment – Arm 1: Ipilimumab Alone

Patients will receive the following treatment until completion of 4 cycles of treatment or meeting one of the criteria in [Section 7.5](#).

Agent	Dose	Route	Day	Schedule*
Ipilimumab	3 mg/kg	IV over 90 mins	1	q 21 days for 4 cycles

* Note: 1 cycle = 21 days

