14.4 Data Submission Overview and Timepoints

- a. WITHIN 24 HOURS AFTER BASELINE blood COLLECTION:

Submit Blood within 24 hours of collection at baseline, as outlined in [Section 15.0](#).

- b. WITHIN 7 CALENDAR DAYS AFTER REGISTRATION:

Submit the following:

S1616 Onstudy Form

S1616 Baseline Abnormalities Form

Baseline Tumor Assessment Form (RECIST 1.1)

Pathology Report documenting histologic confirmation of melanoma*

Submit radiology reports from all scans performed to assess disease at baseline.*

*NOTE: Upload reports via the Source Documentation: Baseline form in Rave®.

- c. WITHIN 21 to 35 CALENDAR DAYS AFTER REGISTRATION:

Submit tissue specimens as outlined in [Section 15.0](#).

Note: Blood for PBMCs must be submitted **within 24 hours of collection** at Day 28 (+/-) 7 calendar days.

- d. WITHIN 14 CALENDAR DAYS AFTER EACH CYCLE OF TREATMENT

Submit the following:

S1616 Treatment Form

S1616 Adverse Event Form

e. WITHIN 14 CALENDAR DAYS AFTER EACH DISEASE ASSESSMENT UNTIL PROGRESSION/RELAPSE (SEE STUDY CALENDAR FOR SCHEDULE):

Submit the following:

Follow Up Tumor Assessment Form (RECIST 1.1)

Submit radiology reports from all scans performed to assess disease.*

*NOTE: Upload reports via the Source Documentation: Follow-Up form in Rave@.

f. WITHIN 14 CALENDAR DAYS AFTER DISCONTINUATION OF TREATMENT:

Submit the following:

S1616 Off Treatment Notice

S1616 Treatment Form

S1616 Adverse Event Form

g. WITHIN 14 CALENDAR DAYS AFTER PROGRESSION:

Follow Up Tumor Assessment Form (RECIST 1.1)

Submit radiology reports from all scans performed to assess disease.*

*NOTE: Upload reports via the Source Documentation: Follow-Up form in Rave@.

h. AFTER PROGRESSION, SUBMIT EVERY 6 MONTHS FOR THE FIRST 2 YEARS AND THEN ANNUALLY UNTIL 3 YEARS FROM REGISTRATION:

Submit the following:

Advanced Melanoma Follow Up Form

Late Effects Form (if prior to treatment for progression or relapse or a second primary, and prior to non-protocol treatment, the patient experiences any severe [Grade \geq 3] long term toxicity that has not been previously reported)

i. WITHIN 4 WEEKS AFTER KNOWLEDGE OF DEATH:

Submit the Notice of Death documenting death information.

Also submit:

If the patient was still on protocol treatment, the materials specified in [Section 14.4e](#).

or

Advanced Melanoma Follow-Up Form (if the patient was off protocol treatment)

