requirement window has been extended to **90** calendar days rather than the normal 30 day requirement.] If there is any question about the reportability of an adverse event or if on-line CTEP-AERS cannot be used, please telephone or email the SAE Specialist at the Operations Office, [name] or [contact], before preparing the report.

CLOSED EFFECTIVE 07/15/2020

**Table 16.1
Late Phase 2 and Phase 3 Studies: Expedited Reporting Requirements for Adverse Events that Occur on Studies under a CTEP IND within 90 Calendar Days of the Last Administration of the Investigational Agent/Intervention¹ Ipilimumab and Nivolumab (Arm 1 and Arm 2)**

FDA REPORTING REQUIREMENTS FOR SERIOUS ADVERSE EVENTS (21 CFR Part 312) NOTE: Investigators MUST immediately report to the sponsor (NCI) ANY Serious Adverse Events, whether or not they are considered related to the investigational agent(s)/intervention (21 CFR 312.64)
 
An adverse event is considered serious if it results in ANY of the following outcomes:
 
 1) Death 2) A life-threatening adverse event 3) An adverse event that results in inpatient hospitalization or prolongation of existing hospitalization for ≥ 24 hours 4) A persistent or significant incapacity or substantial disruption of the ability to conduct normal life functions 5) A congenital anomaly/birth defect. 6) Important Medical Events (IME) that may not result in death, be life threatening, or require hospitalization may be considered serious when, based upon medical judgment, they may jeopardize the patient or subject and may require medical or surgical intervention to prevent one of the outcomes listed in this definition. (FDA, 21 CFR 312.32; ICH E2A and ICH E6). 				

ALL SERIOUS adverse events that meet the above criteria MUST be immediately reported to the NCI via CTEP-AERS within the timeframes detailed in the table below.
				
Hospitalization	Grade 1 Timeframes	Grade 2 Timeframes	Grade 3 Timeframes	Grade 4 & 5 Timeframes
Resulting in Hospitalization ≥ 24 hrs	10 Calendar Days			24-Hour 5 Calendar Days
Not resulting in Hospitalization ≥ 24 hrs	Not required	10 Calendar Days		

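### Arm 1 has no unconditional toxicity or laboratory check after the fourth ipilimumab dose, so laboratory-only and non-serious late events may be under-recorded relative to Arm 2

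*Combined protocol and SAP*

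**What the plan says.** - **Arm 1 dosing.** Section 7.2 gives ipilimumab "q 21 days for 4 cycles".
- **Arm 1 checks.** In calendar 9.1 the row "Toxicity notation" is marked at Weeks 1, 3, 6 and 9, as are blood counts, liver tests, creatinine and TSH. In both follow-up columns toxicity, counts, liver tests and creatinine carry footnote P: "Every 3 weeks until resolution of adverse events". TSH has no follow-up mark. Week 12 carries only disease assessment. The 12-weekly follow-up before progression (footnote N) covers history and physical, weight and performance status, and scans.
- **Arm 2 checks.** Calendar 9.2 has the same marks in Cycles 1 to 4, with the rows "Nivolumab 1 mg/kg" and ipilimumab dosed for the fourth time in Week 10. Calendar 9.3 then puts toxicity, counts, liver tests, creatinine and TSH at Weeks 13, 17, 21 and each later cycle. Off treatment its footnote P has the same condition as Arm 1, at 4-week intervals.
- **Late onset.** Section 8.7 says that "immune-related AEs commonly started within 3 to 10 weeks from first dose". The ipilimumab safety list in Section 3.1c adds that "a minority occurred weeks to months after discontinuation of ipilimumab especially with the initiation of additional treatments".
- **Reporting.** Section 16.1e extends expedited reporting after the last dose to 90 "calendar days rather than the normal 30 day requirement". Section 14.4 asks for an Adverse Event Form after each cycle and after discontinuation. It places the Late Effects Form under "AFTER PROGRESSION, SUBMIT EVERY 6 MONTHS FOR THE FIRST 2 YEARS AND THEN ANNUALLY UNTIL 3 YEARS FROM REGISTRATION".
- **Analysis.** Objective 1.2d and Section 11.3 describe toxicity within each arm.

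**The concern.** The checks at Weeks 3, 6 and 9 come just before doses 2, 3 and 4, so each of the first three doses is followed by a fixed check. In Arm 1 the fourth is not, unless the patient already has an open event. The same holds for anyone in either arm who stops early with no open event. Section 8.7 describes hepatic immune events as mostly silent and found through laboratory tests, and this is the kind of event that an unscheduled period does not find.

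At stake is the Arm 1 toxicity profile (objective 1.2d), which has a thinly observed period after the last dose. Readers of a randomized trial will also set the two columns of toxicity rates beside each other, and Section 11.3 states no ascertainment window that would warn them.

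**Working it through.** **Timing**

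1. Dose day = 1 + 21 × (k − 1) for k = 1 to 4, which gives days 1, 22, 43 and 64. Day 64 is the first day of Week 10. In the text as extracted, the Arm 1 treatment row appears one column late. Section 7.2 and the matching Arm 2 row both give Week 10, and either reading is after Week 9.
2. Week 9 ends on day 63, so the last unconditional Arm 1 set precedes dose 4.
3. The 90-day window after dose 4 ends on day 64 + 90 = 154, the last day of Week 22.
4. Weeks 13, 17 and 21 start on days 85, 113 and 141, all inside that window.

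| After dose 4, to day 154, no open event | Arm 1 | Arm 2, continuing nivolumab |
|---|---|---|
| Unconditional toxicity and laboratory sets | 0 | 3 |
| Unconditional TSH | 0 | 3 |

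**Forms**

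5. Cycle 4 ends on day 84, so its Adverse Event Form is due by day 84 + 14 = 98. The 14 days is a submission deadline and does not itself limit which Cycle 4 events count.
6. From day 98 to day 154 is 56 days. In that span an Arm 1 patient who has not progressed has no routine toxicity form due.
7. The Late Effects Form is requested only after progression, but its condition covers Grade 3 or higher toxicity that arose before any treatment for progression. Some of this toxicity may therefore be recovered once a patient progresses. Under Section 11.2 (exponential, 3-month median) the proportion progression-free is 0.5^(t/3), with t in months of 30.44 days. Day 98 is 3.22 months, giving 48%, or about 10 of 21. Day 154 is 5.06 months, giving 31%, or 6 to 7 of 21.

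**Scale against the plan's precision**

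8. Section 11.3 gives 95% half-widths of 12.3% and 21.4%. The formula 1.96 × √(0.25/n) gives 12.35% at n = 63 and 21.39% at n = 21, so these figures reproduce.
9. The documents give no rate for toxicity that starts only after Week 9. As an illustration only, suppose that a share f of affected Arm 1 patients had such an onset and it was never recorded. The shortfall is then the true rate p × f.

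| True rate p (assumed) | Shortfall, f = 10% to 30% | Half-width at n = 21 |
|---|---|---|
| 20% | 2 to 6 points | 17.1 points |
| 30% | 3 to 9 points | 19.6 points |
| 50% | 5 to 15 points | 21.4 points |

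On these assumptions the shortfall is smaller than the sampling error. It runs in one direction, however, and the confidence interval does not allow for it.

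**The case against.** Much of the case on the other side stands.

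- **No planned comparison is broken.** Section 11.3 assesses toxicity in each arm separately. A reader might infer that a between-arm analysis is biased, or that the rates simply cannot be compared. The plan contains no such analysis, so what suffers is interpretation.
- **The asymmetry follows from continued treatment.** The Week 9 and Week 10 order is the same in both arms, and Weeks 13, 17 and 21 are on-treatment visits. Longer exposure is also a genuine reason for more toxicity in Arm 2.
- **Late toxicity is not simply missed.** The Cycle 4 and off-treatment Adverse Event Forms capture recognised events, and expedited reporting captures serious ones for 90 days in both arms. But forms record what was noticed; they do not order a blood test.
- **Usual onset is mostly covered.** Three to ten weeks is days 21 to 70, largely within the Week 3, 6 and 9 checks. Only a minority of events are said to start after ipilimumab stops.
- **Footnote P is ambiguous.** It lacks the restrictive wording of footnotes B, C, D, H and J. Section 9.0 also refers to group guidelines that are not in the documents and might fill the gap. This argues for clarifying the footnote, and it does not help TSH, which has no follow-up mark.
- **The Background does not depend on this.** A reader might infer that an inflated toxicity excess would distort the case for reserving the combination for salvage use. Section 2.0 ties that case to longer PFS with a high response rate and takes the toxicity as known.

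**Conclusion.** The point holds in a limited form. As written, an Arm 1 patient without an open event has no fixed toxicity or laboratory check after the fourth dose. A continuing Arm 2 patient has three in the same 90 days. Laboratory-only and non-serious events after dose 4 may therefore be under-ascertained in Arm 1, and in early stoppers without an open event in either arm. The laboratory gap can affect every Arm 1 patient who receives dose 4 and has no open event, at most 21. The gap in routine forms is narrower, because it depends on remaining progression-free.

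This weakens the Arm 1 toxicity profile and makes a side-by-side reading of the Section 11.3 rates misleading. The documents do not support saying that late immune toxicity is missed altogether or that the excess for the combination is inflated by any stated amount. The conclusion assumes no dose delays, the literal reading of footnote P, and no stricter requirement in the group guidelines.

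**What to change.** 1. **Calendars.** Reconcile 9.1, 9.3 and their footnotes P with the 90-day window in Section 16.1 and the late-onset statements in Sections 3.1c and 8.7. Post-treatment toxicity ascertainment should follow one stated rule in both arms, whether or not an event is open. The sponsor sets the schedule.
2. **Forms.** In Section 14.4, reconcile the heading over the Late Effects Form with the form's own condition, which concerns toxicity before treatment for progression. Carry routine adverse event form collection through the 90-day window.
3. **Analysis.** In Section 11.3, report toxicity by arm over a window in which both calendars are the same: registration to the end of Week 12. Extend it to the 90-day tail only if item 1 is adopted. Keep the full-period table as supplementary, with the difference in ascertainment stated.

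The cost is minor site workload for at most 21 control patients plus early stoppers, and a possibly slightly higher recorded toxicity rate in Arm 1. The document is marked closed, so items 1 and 2 may come too late for some patients. Item 3 needs no new visits and remains useful regardless.
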